### *Group 2 (single dose FMT): Visit will occur in a clinical setting*

Capsules will be delivered to the patient by a blinded member of the treatment team 48-72 hours following antibiotic treatment completion. If the patient is discharged he/she will be asked to return to the clinic 48-72 hours following completion of his/her antibiotics to consume the 30 capsules under supervision of a nurse or physician. Study staff do not need to collect a blood sample to monitor for neutropenia. During this visit the following will occur:

- Vitals collection
- Physical exam
- Clinical symptoms assessment
- Diet assessment
- Concomitant medications
- Stool sample
- FMT dosing
- Adverse events assessment
- 30 minute post-dose observation

### *All subjects:*

All subjects will provide stool samples every three days after the baseline visit until their FMT intervention is complete and weekly for one month following conclusion of FMT treatment. Patients will also be asked to complete a patient diary daily from enrollment through the first month of follow-up. If a subject is discharged during the study period, he/she will be asked to complete the patient diary from home as well as provide stool samples to be mailed back to the lab for processing. A member of the study team will also call or email patients on a weekly basis during the intervention and follow-up period to remind to complete the stool sample

as well as record any adverse events. If a patient is discharged, vital signs, general health status, and medications at discharge will be assessed through the medical record.

At the end of the 1 month follow-up (last week of providing the weekly, post-FMT stool samples), patients will receive a call assessing the following:

- Clinical assessment by study nurse or physician, specifically evaluating adverse events related to the intervention.
- Data collection at visit:
  - Interim medical history with focus on infectious diseases
  - Concomitant medication
  - Significant changes in diet
  - Changes in stool consistency (Bristol Stool Scale) and frequency
  - General health status
  - Adverse events (NIH criteria)

A table of all study events is provided in Appendix II, 17.2 (Study Calendar).

### **11.3. Unscheduled Visits/Data Collection**

If a patient develops CDI or related serious adverse event, an unscheduled visit will take place and the patient will be treated with standard recurrent CDI care by the treatment team. The development of a CDI will also result in early termination of the patient's study participation, and early termination procedures should be conducted. Other serious adverse events will be evaluated on a case-by-case basis for continuation versus termination of participation.

If a patient develops an infection (besides any he/she was admitted for) with a MDRO, the study team will track the duration of the infection. Any changes to the type of antibiotic, duration, and dosage will be noted as well.

Data points for infectious episode:

- Date
- Preliminary diagnosis
- Physical exam and vital signs
- Changes to diet
- Clinical symptoms questionnaire
- Method of testing for pathogen and pathogen(s) identified
- Sites from which organism was isolated and whether clinical specimens were collected from infection site
- Antibiotic(s)
  - Name
  - Dosage
  - Prescribed duration
  - Final (actual) duration of antibiotics
  - Change in antibiotics regimen
- Concomitant medication (Name, dose, route of administration, duration)
- Hospital admission (yes/no)
  - Name of facility
  - Department where participant was admitted (ward / step down/ ICU)

- Relevant medical procedures
  - Colonoscopy (including preparation)
  - Intestinal surgery
  - Dialysis
  - Other
- Final diagnosis

Data points collected at both the early termination and unscheduled visit only need to be recorded once to avoid duplication. This may include vitals, changes to diet, etc.

#### **11.4. Early Termination**

In the case of an early termination, all study procedures will stop. Study staff will attempt to collect patient diary and a final stool sample. The following will be assessed:

- Clinical assessment, including vital signs if visit is done in person
- Data collection
  - Changes to dietary history
  - Discharge diagnosis
  - Stool consistency and frequency
  - Changes to concomitant medications
  - Clinical symptoms
- Stool sample collection or peri-rectal swab (only if participant is unable to provide a stool sample at in-person visit)

Early termination procedures may be done over the phone or in person if the early termination is occurring during an unscheduled visit. Participants will be asked if study staff may follow participants passively using the medical record if clinical follow-up and/or stool collection is not viable.

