### 7.2.3. Primary Safety Outcome Measures

1. Proportion of participants with an adverse event (AE) occurring during any point of the study following randomization.
2. Proportion of participants with a severe adverse event (SAE) occurring during any point of the study following randomization.
3. Proportion of participants with newly acquired transmissible infectious diseases which are considered adverse events of special interest (AESI) after randomization.

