##### **8.6.2.1. *Data Collection and Follow-up for Withdrawn Subjects***

If the subject is willing, the coordinator will ask to schedule a close-out study visit to collect a final stool sample and follow-up safety evaluation.

A subject may withdraw from the study at any time for any reason with no consequences. A participant

may be withdrawn from the study by the Investigator for the following reasons:

- Adverse event that may make it no longer in the best interest of the subject to continue to participate
- Recurrent *C.diff* infection
- Participant's choice
- Protocol violation/ non-compliance
- Pregnancy
- Lost to follow-up
- Other (must be noted)

The primary reason for withdrawal from the study will be recorded. Participants will be encouraged to complete the Early Termination Visit. The Early Termination Visit procedures are listed in Section 11.4. Although participants are free to withdraw at any time, subjects will be encouraged to remain in the study for follow-up safety evaluation. Every attempt should be made to follow all AEs and SAEs ongoing at the time of early withdrawal to resolution or until stabilized. If possible, a final stool sample will be collected at the time of Early Termination. All subjects who are randomized will be included in the safety analysis.

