#### **11.5. Study End**

All subjects will be called 6 months following completion of FMT treatment.

- Data collected during the final study visit call:
  - Changes to medical history
  - Changes in stool consistency (Bristol Stool Scale) and frequency
  - Adverse events (including SAEs, NIH criteria)

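### Sections 11.3 and 11.4 stop all study procedures after a CDI, in conflict with Sections 11.5, 8.6.2.1 and 7.2.3, so new adverse events after a recurrence have no assured active collection

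*Combined protocol and SAP*

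**What the plan says.** The relevant text is spread over several sections of the combined protocol and SAP.

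- **Section 11.3:** "The development of a CDI will also result in early termination of the patient's study participation". It also requires an unscheduled visit for every CDI.
- **Section 11.4:** "In the case of an early termination, all study procedures will stop". The closing list opens with "Clinical assessment, including vital signs if visit is done in person" and goes on to diet, discharge diagnosis, stool pattern, medications, clinical symptoms and a final sample. It names no adverse-event item. On later follow-up it says: "Participants will be asked if study staff may follow participants passively using the medical record if clinical follow-up and/or stool collection is not viable".
- **Section 8.6.2.1:** recurrent CDI is one of the grounds on which a participant "may be withdrawn from the study by the Investigator for the following reasons". A close-out visit with a safety evaluation is offered to willing subjects, events ongoing at withdrawal are followed, and "subjects will be encouraged to remain in the study for follow-up safety evaluation". Every randomized subject enters the safety analysis.
- **Section 11.5:** "All subjects will be called 6 months following completion of FMT treatment".
- **Section 7.2.3:** the safety outcomes are the proportions with an AE, with an SAE, and "Proportion of participants with newly acquired transmissible infectious diseases which are considered adverse events of special interest (AESI) after randomization".
- **Section 11.2:** weekly contacts record adverse events, and the 1-month call evaluates them.
- **Section 17.2 (calendar):** adverse-event assessment is marked for all groups at the unscheduled visit, the 1-month call and the 6-month assessment. There is no early-termination column.
- **Section 12.3:** no rule is given for subjects whose follow-up is cut short.

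**The concern.** Two instructions about the same patient cannot both be followed. A coordinator reading Sections 11.3 and 11.4 would close the patient out after a CDI and make no further calls. One reading Sections 8.6.2.1 and 11.5 would keep calling. Different patients could be handled differently, with no record that this had happened.

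The affected patients are not a random subset. CDI is an outcome that FMT is meant to change, so follow-up for later events would depend on a post-randomization outcome that may differ by arm. The Section 7.2.3 proportions have all randomized patients in the denominator, so a patient lost to active follow-up after CDI with no event recorded counts as event-free.

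There is also a cost inside the FMT arms. Section 5.6.1 concedes that long-term follow-up data on FMT are sparse. Section 13.5.1 suspends the study for any related serious event, including transmission of a donor pathogen. That rule works only if such events are captured in FMT recipients who have had a recurrence.

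**Working it through.** The plan gives no figure on this point to reproduce. The only planning number that bears on it is 3 × 10 = 30 subjects, set by the patients available (Section 12.1).

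**Step 1. What is collected after a CDI.**

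| Event | Provision | Assured? |
|---|---|---|
| Present at the CDI | Unscheduled visit (11.3), with adverse-event assessment in the calendar (17.2) | Yes |
| Ongoing at termination | Followed to resolution or stability (8.6.2.1, 13.4) | Yes, for known events |
| New, at close-out | One safety evaluation (8.6.2.1) | Only if the subject is willing |
| New, later, by call | 1-month and 6-month calls (11.2, 11.5) | Contradicted by 11.4 |
| New, later, by record | Passive review (11.4) | Only with permission, and where clinical follow-up and/or stool collection is not viable |

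The gap lies in the last two rows.

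**Step 2. How many patients.** The inputs are background figures used as assumptions. Section 5.1 gives 24 to 65% recurrence after standard CDI treatment. Section 5.4 gives 83% and 90% success for FMT, hence 17% and 10% failure. Expected terminations per arm = 10 × p:

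- without FMT: 10 × 0.24 = 2.4 to 10 × 0.65 = 6.5
- with FMT: 10 × 0.10 = 1.0 to 10 × 0.17 = 1.7

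**Step 3. How much follow-up is exposed.** Assume a 14-day antibiotic course, 7 further dosing days and 6 months taken as 180 days: T = 14 + 7 + 180 = 201 days. The share of a patient's follow-up after a CDI on day t is (T − t)/T:

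- t = 14: 187/201 = 93%
- t = 30: 171/201 = 85%
- t = 60: 141/201 = 70%

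On the literal reading, with t = 30, the share of an arm's follow-up lost is p × 171/201. That is 20.4% at p = 0.24, 55.3% at 0.65, 8.5% at 0.10 and 14.5% at 0.17.

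**Step 4. Where terminations fall.** Placebo share = p(placebo) / [p(placebo) + p(daily) + p(single)]:

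| Placebo / daily / single | Placebo share |
|---|---|
| Equal rates (no FMT effect) | 33% |
| 24 / 17 / 17% | 2.4/5.8 = 41% |
| 24 / 10 / 10% | 2.4/4.4 = 55% |
| 65 / 17 / 17% | 6.5/9.9 = 66% |
| 65 / 10 / 10% | 6.5/8.5 = 76% |
| 24 / 17 / 24% | 2.4/6.5 = 37% |
| 65 / 10 / 65% | 6.5/14.0 = 46% |

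The last two rows give the single-dose arm the placebo rate, because that arm receives no FMT until 48 to 72 hours after antibiotics end (Section 7.1). Placebo carries more than half of the expected terminations only if its rate exceeds the sum of the other two.

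**Step 5. Direction on the Section 7.2.3 outcomes.** Section 13.1.1 counts any new clinical diagnosis as an adverse event, so a terminated CDI patient would ordinarily already count in the AE proportion, whatever happens later. If the CDI leads to hospital admission or prolongs a stay, the patient also counts in the SAE proportion (Section 13.1.2). Truncation can therefore remove only later events in patients not already counted. If FMT works, CDI itself adds counted events on placebo while shorter follow-up removes later ones. These effects run in opposite directions, and the documents give no event rates with which to net them.

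**The case against.** The best defence is that Sections 11.3 and 11.4 are not the whole plan. Every CDI triggers a visit at which adverse events are assessed, known events are followed, a close-out safety evaluation is offered, record follow-up can be requested, and Section 11.5 makes no exception to the 6-month call. On that view the blunt sentence in Section 11.4 is loose wording about sampling and dosing.

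Part of this stands. It would be wrong to say that adverse events go unassessed when a CDI occurs, or that both calls are certainly lost. It does not settle the matter. Encouragement to remain in the study has little force for a patient whose participation Section 11.3 has ended. The provisions for ongoing events do not reach new ones, and nothing says whether Section 11.4 or Section 11.5 prevails.

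A reader might also infer that the losses fall mainly on placebo. No section says so. At 24% against 17%, expected terminations are 2.4 on placebo and 3.4 across the two FMT arms.

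Finally, this is a pilot with descriptive safety summaries, and the background rates describe other settings: recurrence after standard CDI treatment, and FMT as treatment of recurrent CDI rather than prevention during antibiotics. That limits the weight of the figures but does not remove the contradiction.

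**Conclusion.** The concern holds as an unreconciled contradiction with a real gap in safety collection. Followed literally, Sections 11.3 and 11.4 end the weekly contacts and both safety calls after a CDI. New SAEs, AESIs and other events after that point then have no assured active collection, contrary to Sections 7.2.3, 8.6.2.1 and 11.5.

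On the assumed background rates, roughly 1 to 6.5 patients per arm of 10 would be affected. Each would have 70 to 93% of planned follow-up still to run if the CDI came between day 14 and day 60. If FMT prevents CDI, follow-up per patient would be shorter on placebo.

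A reader might go further and conclude that FMT will look less safe than it is, and attach a number of percentage points. The documents do not support that. They give no SAE risk, hazard or CDI timing, and a CDI itself ordinarily counts as an AE and sometimes as an SAE. The size and net direction of bias on the planned proportions are therefore undetermined.

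**What to change.** 1. Reconcile Section 8.6.2.1 (withdrawal for CDI as a discretion) with Section 11.3 (termination as a consequence), and Section 11.4 with Section 11.5.
2. State in Sections 11.3 and 11.4 that, unless consent is withdrawn, the 1-month and 6-month safety calls continue after early termination, with medical-record review if the patient cannot be reached. Give the date from which the calls are counted when a patient terminates before completing FMT, since Section 11.5 counts from completion.
3. Add an AE, SAE and AESI assessment to the Section 11.4 list. This matters most for terminations by phone or for reasons other than CDI, where no unscheduled visit is guaranteed.
4. Add an early-termination column to the Section 17.2 calendar.
5. Report follow-up time by arm beside the Section 7.2.3 proportions, so that any remaining imbalance is visible.

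The cost is protocol wording and two calls already scheduled, with no new visits or tests. If both FMT arms ran at the FMT figures, about 4 to 10 patients would be involved (2.4 + 2 × 1.0 = 4.4 to 6.5 + 2 × 1.7 = 9.9). There would be more if FMT had no effect (3 × 6.5 = 19.5 at the 65% rate). No view is taken on study product or treatment after a CDI.

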#### **11.5. Study End**

All subjects will be called 6 months following completion of FMT treatment.

- Data collected during the final study visit call:
  - Changes to medical history
  - Changes in stool consistency (Bristol Stool Scale) and frequency
  - Adverse events (including SAEs, NIH criteria)

### **12. STUDY ANALYSIS**

#### **12.1. Sample Size**

A total of 30 subjects – 10 per treatment group – will be recruited into this study. As this is a pilot study, sample size was not driven by a statistical test of hypotheses, instead it was driven by a pool of available patients eligible and willing to participate.

#### **12.2. Subject Population for Analysis**

We plan to enroll 10 patients per group with the goal of having 8 patients per group complete the treatment and be analyzed in the final analysis.

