## 8. STUDY SUBJECTS – ENROLLMENT AND WITHDRAWAL

### 8.1. Subject Population

We plan to enroll 30 subjects, 10 subjects per group, with the goal of having eight analyzable subjects who complete trial in each group. Children under 18 years of age will not be included in this study due to the uncertainty of the safety of the proposed intervention in those under 18 in this population. Participants must

meet inclusion criteria and have no exclusion criteria prior to randomization (described below). We expect the study population to be predominantly Caucasian due to the demographics of Dane County. We expect roughly 14% of the subjects to be minorities and half the subjects to be female. There are no study restrictions based on gender or race/ethnicity. Subjects will be patients at the University of Wisconsin Hospitals and Clinics (UWHC). Two groups of subjects from UWHC will be included in this study, inpatients and/or outpatients. Both study populations will have had a CDI within the last 90 days and are on an antibiotic for an unrelated reason and meeting all additional inclusion criteria listed in section 8.2. Both inpatients and outpatients will be identified through medical record review. Inpatients will always be contacted in a clinical setting while outpatients may be contacted by either mail/phone or in the clinic. Outpatients are included in this study as many infections treated with antibiotics are not severe enough to require hospitalization.

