## **9.8. Modification of Study Intervention/Investigational Product for a Participant**

If the participant is unable to complete the full dose of DE or placebo in one sitting the actual dose ingested will be recorded. Further study product administration, including the remainder of the incomplete dose and scheduled upcoming doses as applicable will be at the discretion of the treating physician. The remaining capsules scheduled to be administered may be offered to the participant on the same day they were scheduled. Intention-to-treat analysis will be utilized according to best practices in clinical trials.

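### No efficacy analysis set is stated: 12.2 and 8.1 tie being analysed to completion, 9.8 says intention-to-treat, and CDI itself ends participation

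*Combined protocol and SAP*

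**What the plan says.** Three places in the combined protocol and SAP bear on who is analysed for efficacy.

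- Section 12.2 (Subject Population for Analysis) is one sentence: enrol 10 per group, "with the goal of having 8 patients per group complete the treatment and be analyzed in the final analysis".
- Section 8.1 has the same target with a different condition: "eight analyzable subjects who complete trial in each group".
- Section 9.8 says "Intention-to-treat analysis will be utilized according to best practices in clinical trials". The paragraph opens with "If the participant is unable to complete the full dose of DE or placebo in one sitting" and deals with incomplete dosing. It does not say which patients or outcomes the principle covers.

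Section 12.3 names no analysis set and no handling of missing data. The only population stated outright is for safety, which is all randomised patients (8.6.2.1).

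On what happens after CDI, 11.3 says "The development of a CDI will also result in early termination of the patient's study participation", and 11.4 adds "In the case of an early termination, all study procedures will stop". Two exceptions follow in 11.4: "Study staff will attempt to collect patient diary and a final stool sample", and "Participants will be asked if study staff may follow participants passively using the medical record" where clinical follow-up or stool collection is not viable. CDI recurrence, and time to it from randomisation, are secondary outcomes in 7.2.2.

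**The concern.** An analyst who relies on 9.8 and one who relies on 12.2 would use different patients, and nothing in the plan says which is right. In most pilots that would be a drafting gap. Here it matters more, because the event that ends participation is itself an outcome. A completer set would select patients after randomisation, partly on CDI. That would distort the CDI comparison directly, and could bias the primary microbiome comparison by leaving out patients whose gut communities may have fared worst.

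A second problem remains even if intention-to-treat is applied throughout. Once procedures stop at CDI, the later weekly stool samples (7.2.1) and adverse events at any point after randomisation (7.2.3) may be missing for exactly these patients. The gaps then depend on an outcome.

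**Working it through.** **1. The plan's own figures.** Enrolled: 3 × 10 = 30. Analysed, if the goal is just met: 3 × 8 = 24. Left out: 30 − 24 = 6, and 6/30 = 20%. That 20% is implied by 8 of 10 and stated nowhere. Section 12.1 gives no power calculation, so there is no sample-size figure to check.

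**2. One patient, three readings.** Take a patient who develops CDI.

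- Under 9.8, applied to all outcomes, the patient stays in the assigned group and counts as an event.
- Under 12.2 read literally, the patient drops out of the analysis if CDI comes before treatment is complete, and stays in if it comes later.
- Under 8.1 read literally, and with 11.3 applied to every CDI, the patient does not complete the trial whenever CDI occurs. CDI among trial completers is then zero in every arm.

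**3. The window for treatment completion differs by arm.** Let L be the antibiotic course in days (sections 2 and 7.1).

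- Daily arms, for L up to 14: complete on day L + 7.
- Single-dose arm, for L up to 14: complete on day L + 2 to L + 3.
- Gap: 7 − 3 = 4 to 7 − 2 = 5 days. For L = 7 this is day 14 against day 9 to 10. For L = 14 it is day 21 against day 16 to 17.
- For courses over 14 days, 8.4.2.2 applies. Its group labels do not match 7.1, and the two must be reconciled. Read by regimen, daily capsules stop at day 14 and the 30-capsule dose falls on day 16 to 17, so the order reverses.

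**4. Effect on the CDI proportion among treatment completers.** Let p be the true CDI proportion in an arm and f the share of CDI that occurs before treatment is complete, with no other dropout. The completer proportion is p(1 − f)/(1 − pf). This is below p whenever f > 0 and 0 < p < 1, because 1 − f < 1 − pf. Understatement within an arm is therefore general.

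**5. Effect on the difference between arms.** This has no general direction. Two assumed cases for daily FMT against placebo only, with equal f in both arms, show it:

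- 24% against 12%, f = 0.50: 0.12/0.88 = 13.6% and 0.06/0.94 = 6.4%. The difference is 7.3 points (from unrounded values) against a true 12.0. With f = 0.25 it is 9.9 points and with f = 0.75 it is 4.0.
- 65% against 50%, f = 0.25: 0.4875/0.8375 = 58.2% and 0.375/0.875 = 42.9%. The difference is 15.4 points against a true 15.0.

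The 24% and 65% are the ends of the recurrence range in 5.1. The FMT proportions and f are assumptions. Unequal f could move the difference either way. The 5.1 range has no timing and describes recurrence despite metronidazole or vancomycin, whereas trial patients have finished CDI therapy and may be up to 90 days past the episode (8.2).

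**6. The single-dose arm.** Completing treatment there means taking the one dose. Any CDI that prevents completion precedes all FMT, so FMT cannot have changed it. The cases in step 5 do not apply to that arm.

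**7. Data after CDI.** Section 8.6.2.1 lists recurrent CDI as a permitted reason for withdrawal and encourages safety follow-up. Section 11.3 makes termination automatic. Section 11.4 stops procedures, with the exceptions above. Section 11.5 has every subject called at 6 months. These cannot all be followed for a patient with CDI who still consents.

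**The case against.** The strongest reply is that 9.8 already names intention-to-treat without an explicit limit, while 12.2 and 8.1 state goals and nowhere say that non-completers are excluded. The outcome definitions point the same way. Section 7.2.2 counts CDI over the course of the study with time from randomisation, 11.3 schedules a visit and data collection when CDI occurs, and a trial-completer set would have no CDI events to analyse, which the authors can hardly have meant. Section 2 names linear mixed models, which can use incomplete series. The study is also a 30-patient pilot with CDI secondary.

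Much of this stands. A reader might infer that the plan commits to dropping patients with CDI. It does not: the completer wording is a goal, and the harm to the CDI comparison does not arise if 9.8 governs every outcome. A reader might also infer that a completer analysis would always shrink the difference between arms, or would remove half as many patients from each FMT arm as from placebo. Steps 5 and 6 show that neither follows. Nor are patients with CDI lost entirely, given the attempted final sample, the possible record follow-up and the all-randomised safety set.

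What does not fall is the conflict itself. The section that should define the population links being analysed to completing, the intention-to-treat sentence sits elsewhere in a dosing paragraph, and literal readings give different denominators. The stop rule in 11.3 and 11.4 also leaves outcome-dependent gaps that naming intention-to-treat does not fill.

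**Conclusion.** The point holds as a conflict of wording and a missing definition, and should be fixed before analysis. No stated figure is wrong. If a completer set were used, CDI would be understated in any arm with early CDI, and would be zero among trial completers if 11.3 is applied as written. Selection would run over windows that differ by 4 to 5 days between regimens for courses up to 14 days. The between-arm difference could be distorted in either direction. Its size cannot be estimated, because the documents give neither the timing of CDI nor a rate for this population; the figures in step 5 show only that the direction is not fixed.

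The consequence is for interpretability, not power. Confidence is medium, because the authors may well have intended intention-to-treat throughout.

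**What to change.** **Analysis set.**

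- In 12.2, state that microbiome, CDI and colonisation outcomes are analysed in all randomised patients by assigned group.
- Use all available samples in the linear mixed model named in section 2, and count every CDI as an event.
- Make completers a sensitivity set, saying whether that means completers of treatment or of the trial.
- Keep 8 per group as a retention target only, and align 8.1 and 9.8.

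This is a wording change.

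**Data after CDI.** Reconcile 8.6.2.1, 11.3, 11.4 and 11.5 so that patients with CDI who still consent keep the adverse-event calls, the 6-month call and passive record follow-up. Continued stool sampling after CDI is optional, since such samples also reflect CDI treatment. If it is done, flag those samples and leave them out in a sensitivity analysis. This is a small separate amendment and costs a few extra calls.

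The group labels in 8.4.2.2 and 7.1 should be reconciled at the same time, because they determine when treatment counts as complete. Nothing here addresses CDI care or study-product decisions.
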